Stimulation parameters (amplitude, frequency, and pulse width) are programmed after surgery and at follow-up intervals, and the efficacy of DBS depends on finding parameters that reduce symptoms without causing side effects. However, there are over 42,000 available combinations of amplitude, frequency, and pulse width in the IPG, and few data describing the relationships between stimulation parameters and clinical outcomes. As a result, the selection of stimulation parameters is an ad hoc process, with associated difficulties of time, expense, and patient discomfort. Further, the patient is often deprived of the optimal benefits of stimulation until this time consuming process leads to efficacy.

Application of each DBS pulse results in activation of a population of neurons around the electrode. This evoked neuronal activity creates a signal -- the DBS local evoked field potential (DLEP) -- that can be recorded with two of the four contacts on either the clinical DBS electrode or a second electrode. Thus, this intraoperative recording approach does not require implantation of any electrical hardware. The magnitude and character of the DLEP response will reveal the type and spatial extent of neuronal element activation during stimulation, including between brain regions, such as between subthalamic nucleus (STN) and globus pallidus externa (GPe). Our previous work exploring the mechanisms of action of DBS revealed a very strong correlation between the number and type of activated neurons and clinical efficacy during variation in stimulation intensity [Kuncel et al, 2007; Kent et al, 2015]. Therefore, we expect a strong correlation between the recorded DLEP and the changes in symptoms during DBS. Spontaneous, local field potentials (LFPs) are also recorded using the same methods described above. LFPs are signals measured with electrode contacts that are continuously generated by ongoing neural activity, whereas DLEPs are short-duration signals evoked immediately following stimulation pulses. Together, DLEPs and LFPs are a potential biomarker for disease state and severity in PD, which we will

test initially intraoperatively and long-term using the RC+S IPG for scalar closed-loop control of the DBS parameters.

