The data set will consist of recordings of neural and/or LFP recordings, and either mouse click timing data for measurement of bradykinesia in Parkinson's disease subjects or tremor accelerometry data for patients with Parkinson's disease. The DLEP recordings will be serially averaged with stimulus-triggering to remove random noise while preserving the evoked response. The signal-to-noise ratios of DLEP recordings will be compared across data sets to determine which combination of stimulation and recording sites maximize recording quality. We will quantify performance on the mouse click timing task by the delay between key presses and the time each key is held. Tremor will be quantified by calculating the total power within a window of the power spectrum of the time series of the tremor. We will perform ANOVA and post-hoc statistical analysis, in which the amplitude, frequency, and contact configuration used for stimulation will be the independent variables, and with dependent variables describing bradykinesia, tremor, and DLEP characteristics. We will also calculate correlation coefficients between tremor or bradykinesia and DLEP characteristics. Data and statistical analyses will be conducted by the study team, including the study statistician, [name] (Associate Professor of Biostatistics and Bioinformatics).

Additionally, clinical study staff may use pre- and post-operative brain imaging to determine the location of implanted DBS electrode contacts. The only data generated from this analysis will be a determination of the location of the contacts used to record neural activity (DLEPs and/or LFPs) relative to the brain region targeted for stimulation. Other study staff will analyze DLEP and/or LFP recordings obtained during surgery to generate a prediction of recording contact location prior to imaging analysis for each subject, and clinical study staff will be blinded to these predictions during imaging analysis.

Subjects will be included in data analysis if DBS is clinically effective at reducing motor symptoms for particular stimulation parameters, and DLEP and/or LFP data are observed during at least one trial.

[name] and [name] [name] conduct a total of 4-6 new DBS implants for PD per month. We have recruited approximately 1 subject per month at Duke over the past 18 months to participate in other intraoperative studies. Thus, we expect to recruit a maximum of 32 subjects during the course of this study at Duke University.

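### The analysis set is conditioned on an undefined motor response that is itself analysed, and the same condition governs recording analyses that need no motor benefit

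*Combined protocol and SAP*

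**What the plan says.** The rule, under Data Analysis and Statistical Considerations, has two conditions, both of which must be met. The first concerns efficacy: "Subjects will be included in data analysis if DBS is clinically effective at reducing motor symptoms for particular stimulation parameters". The second concerns the neural signal and requires only that "DLEP and/or LFP data are observed during at least one trial". The rule is worded for data analysis as a whole, with no exception for any analysis.

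The same section plans:
- an ANOVA "in which the amplitude, frequency, and contact configuration used for stimulation will be the independent variables", with bradykinesia, tremor and DLEP measures as dependent variables;
- a correlation: "We will also calculate correlation coefficients between tremor or bradykinesia and DLEP characteristics";
- a recording-quality analysis: "The signal-to-noise ratios of DLEP recordings will be compared across data sets", to find the best stimulation and recording sites;
- a blinded location exercise, in which staff use the signals to "generate a prediction of recording contact location prior to imaging analysis for each subject".

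Purpose of the Study and Study Design and Procedures add a comparison of the Duke circuitry with the RC+S test system, alternating the two on the same leads.

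Background and Significance gives the hypothesis: "Therefore, we expect a strong correlation between the recorded DLEP and the changes in symptoms during DBS".

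The documents do not define clinical effectiveness. The clinician's judgement in Study Design and Procedures sets only the amplitude ceiling. No analysis of all attempted subjects and no count of exclusions is planned.

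**The concern.** Change in motor symptoms is what the ANOVA and the correlation are meant to describe. A rule that admits subjects according to that change selects on the outcome, whether the judgement comes from the study trials or from separate clinical testing. The subject with a clear DLEP and no motor benefit is the most informative case against the hypothesis, and is the one the rule can remove without a trace.

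Because no threshold or assessor is fixed, the set can also be settled after the data are seen. With at most 32 subjects, a few discretionary exclusions matter.

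The rule further reaches the signal-to-noise, device and location analyses. There a good recording would be discarded for a reason unrelated to its quality.

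**Working it through.** The plan has no figure to reproduce. The 32 is an enrolment maximum, with no alpha, power, effect size, SD or expected exclusion rate. The check is therefore of the text, followed by an illustration of size.

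**Text.** Motor response enters the ANOVA and the correlation directly. It does not enter the by-site signal-to-noise comparison, the Duke versus RC+S comparison or the location prediction, yet the rule covers all of them. The signal condition is lenient: one trial with either signal suffices, and the Background says "LFPs are signals measured with electrode contacts that are continuously generated by ongoing neural activity". The efficacy condition is the one that matters.

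**Inputs from the documents.** About 45 minutes of data collection; 2-minute tremor trials and 10-minute bradykinesia trials. With no gaps, 45/2 gives 22 tremor trials and 45/10 gives 4 bradykinesia trials. Maximum enrolment is 32.

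**Assumed, not in the documents.** Effective means at least one study trial with a 30% or greater reduction, that is, log improvement of at least t = −ln 0.7 = 0.357. Trial log SD σ is 0.2 or 0.3. Non-responders are 20% of subjects. A responder improves by −ln 0.6 × u = 0.511u at setting intensity u between 0 and 1; a non-responder by 0. DLEP = u + noise (SD 0.2).

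**Who qualifies.** A true non-responder qualifies by noise with probability 1 − Φ(t/σ)^k over k trials:
- σ = 0.2: Φ(1.78) = 0.963, giving 14% for k = 4 and 57% for k = 22.
- σ = 0.3: Φ(1.19) = 0.883, giving 39% for k = 4 and 94% for k = 22.

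The filter therefore acts very differently in the two motor subtypes.

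**ANOVA intensity effect** (within-subject slope of improvement on u, by simulation). Across all subjects it is 0.8 × 0.511 = 0.409.

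| Trials, settings | σ = 0.2 | σ = 0.3 |
|---|---|---|
| 4, random u | +30% | +22% |
| 4, evenly spaced up to u = 1 | +25% | +18% |
| 22, random u | about +10% | +1% |

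- If separate testing identified responders exactly, the figure would be 1/0.8 = 1.25, or +25%.
- A slope pooled across subjects (4 trials) gives +24% and +15%: same direction, smaller.
- Other assumptions, random u: 10% non-responders give 14%–18% (4 trials) and 1%–5% (22). With 20% non-responders, a 20% threshold gives 10%–15% and at most 1%; a 40% threshold gives 42%–55% and 8%–22%.
- With no effect in anyone, the slope stays within about 0.003 log units of zero.

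**Correlation, direction 1: narrower range of response.** Take a mean improvement of 25%, between-subject log SD 0.25 and true r = 0.50. The between-subject r in the selected set is 0.39–0.42 with 4 trials (23%–32% of subjects dropped) and 0.44–0.47 with 22 (4%–13% dropped). For scale, the Fisher interval for r = 0.50 with n = 32 is tanh(0.549 ± 1.96/√29) = tanh(0.549 ± 0.364) = 0.18 to 0.72. The shifts, at most 0.50 − 0.39 = 0.11, are smaller than that sampling error.

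**Correlation, direction 2: non-responders who do show a DLEP.** With 4 trials, within-subject r rises from about 0.40 to 0.49 (σ = 0.2) or 0.30 to 0.34 (σ = 0.3). With 22 it rises from 0.40 to 0.43, or stays at 0.30. If those non-responders show no DLEP (counted as zero), the pooled r with 4 trials falls instead, from 0.54 to 0.50 or 0.41 to 0.38.

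**Precision of the device comparison.** If 20% were excluded, about 26 of 32 subjects remain (32 × 0.8 = 25.6). Standard errors of per-subject contrasts grow by √(32/26) = 1.11.

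**The case against.** A mechanistic study may reasonably concentrate on effective stimulation. Risk / Benefit Analysis allows sedation as needed provided symptoms are still present, so the rule may partly be meant to screen out sessions in which symptom change could not be measured. That stands as a reason for a validity rule on motor measurements. It does not justify using response to stimulation as the entry criterion for every analysis.

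The sizes rest on assumed thresholds, response rates and SDs. That is also true; only the trial and session lengths come from the documents.

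A reader might infer more than the text supports:
- *That the results would describe responders only.* With 22 trials, 57%–94% of true non-responders still qualify under the assumptions above. Ineffective trials in an included subject also appear to stay in, since benefit at some setting is enough.
- *That the rule always inflates the DLEP–symptom correlation.* It can lower or raise it.
- *That it biases Duke against RC+S.* The two systems alternate on the same leads, so dropping a subject normally loses both sets of recordings. That costs precision, and no between-system bias is shown. Nor do the documents say the systems will be compared on signal-to-noise ratio; the stated purpose of that comparison is by site.
- *That the filter is certainly a study measurement.* Its source is unstated, which is part of the problem.

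Application to the location exercise is also a reading of the rule as written, because predictions are described as made for every subject.

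**Conclusion.** The concern holds as a cheap improvement. The text establishes that an undefined motor response is a condition for all data analysis, that motor response is also analysed, and that neither an all-attempted analysis nor an exclusion count is planned.

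The size is illustrative. With 20% non-responders, a 30% threshold and trial log SD 0.2–0.3, the within-subject ANOVA intensity effect is overstated by about 18%–30% with 4 bradykinesia trials and about 1%–10% with 22 tremor trials. Randomised parameter contrasts are essentially undistorted if stimulation has no effect in anyone. The correlation may shift in either direction, and the range-narrowing shifts are below sampling error at n = 32. The selected set is enriched for responders, most strongly when trials are few or when separate testing is accurate.

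**What to change.** Drop motor benefit as a condition for analysis, and match each analysis to the data it needs:
- signal-to-noise, device and contact-location analyses: all subjects with attempted recordings (location also needs imaging);
- ANOVA and correlation: all subjects with valid motor and DLEP data, non-responders included.

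Define two validity rules in advance, both independent of response to stimulation. For a technically valid recording, a valid trace with no DLEP stays in as a low or zero response, and only technical failure is missing. For a valid motor measurement, require a measurable symptom in the stimulation-off phase.

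Keep the present responder and signal-present set as a labelled sensitivity analysis, with clinical effectiveness defined beforehand by measure, threshold, assessor and time point. Report the number excluded by each condition and by motor subtype.

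The cost is about a paragraph of text and a little more analysis work, with no extra subjects or procedures. The downside is that results may look less favourable.
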